## Subject Information

*Target accrual is the proposed total number of subjects to be included in this study at Mayo Clinic. A "Subject" may include medical records, images, or specimens generated at Mayo Clinic and/or received from external sources.*

Target accrual: 20 healthy adults

Subject population (children, adults, groups): Adults aged 18-45

### Inclusion Criteria:

- Age 18-45
- Healthy adults with no medical conditions or previous injuries, trauma, or surgeries that reduce your balance, mobility or strength
- Able to follow simple directions
- Willingness to participate in the study
- No restriction will be placed on gender, race, or ethnicity

### Exclusion Criteria:

- Current or chronic pain in your shoulders, elbows, hips, knees, ankles, feet, neck or back
- Use of assistive device such as walker or cane

## Data Analysis

*Power analyses may not be appropriate if this is a feasibility or pilot study, but end-point analysis plans are always appropriate even if only exploratory. Provide all information requested below, or provide justification if not including all of the information.*

**Power Statement:** 20 subjects will each perform 50 trials (1000 data points for each treadmill). With 1000 data points, we can accurately estimate the limits of agreement to within  $+\/- 1.96 \sqrt{2 \left( \frac{3}{n} \right)}$  s or  $+\/- 0.11$  standard deviations (Bland and Altman, *Lancet*, i:307-10, 1986).

**Data Analysis Plan:** Data will be analyzed using custom software (MATLAB, Mathworks, Natick, MA). The following dependent variables will be recorded for each visit:

- Treadmill belt displacement
- Treadmill belt peak velocity
- Treadmill belt average initial acceleration
- Treadmill force
- Treadmill moment
- Center of pressure location and excursion

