## Research Question and Aims

**Aims, purpose, or objectives:** The purpose of this study is to evaluate the accuracy with which a programmable treadmill delivers controlled postural disturbances under real world use scenarios (i.e., with a subject on the treadmill belt).

**Hypothesis:** We hypothesize that the observed disturbance parameters will show acceptable agreement with the command disturbance parameters. In other words, a Bland-Altman plot 95% confidence interval of differences between input and observed characteristics will contain zero.

**Background (Include relevant experience, gaps in current knowledge, preliminary data, etc.):** Compensatory step training safely induces a fall by delivering large postural disturbances, in turn requiring subjects to arrest a fall through timely well-placed steps and reduced trunk rotation (Owings et al., *Clin Biomech.* 16:813-9, 2001; Crenshaw et al., *J Biomech.* 45:129-33, 2012). Such training has reduced falls in the laboratory (Grabiner et al., *Med Sci Sports Exerc.* 44:2410-4, 2012) and free-living environment (Rosenblatt et al., *JAGS*, 61:1629-31, 2013, Kaufman et al., *Clin Orth Related Res.* 472:3076-3084, 2014). The ability to respond to a disturbance without stepping (Pai et al., *J Biomech.* 31:1111-1118, 1998) or by taking only one step (Rogers et al., *J*

*Gerontol.* 56A:M589-M594, 2001; Hilliard et al., *Arch Phys Med Rehabil.* 89:1708-1713, 2008) is reduced for individuals who fall compared to non-fallers. These results suggest that assessments that focus on the ability to respond to external disturbances have utility in prospectively identifying fallers. Such assessments and interventions, however, must use equipment that precisely delivers postural disturbances of various magnitudes. The purpose of this study is to evaluate the accuracy with which a programmable treadmill delivers controlled postural disturbances. The new treadmill (Treadmetrix, Park City, UT) is instrumented with force sensors and has been custom programmed to deliver postural disturbances in a similar manner to treadmills previously validated under IRB 14-000939 from the same PI.

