### Study Design and Methods

**Methods:** *Describe in lay terms, completely detailing the research activities that will be conducted by Mayo Clinic staff under this protocol.*

Subjects will participate for a single 2 hour visit in the Motion Analysis Laboratory. Subjects will be asked to wear comfortable athletic shoes and clothing. Subjects will give written informed consent. A study team member will ask the subject questions about their medical history to see if they qualify for the study. These questions (with required answers) are as follows:

- What is your age? (Age must be between 18 to 45 years)
- Do you have current or chronic pain in your shoulders, elbows, hips, knees, ankles, feet, neck or back? (no)
- Do you have any medical conditions or previous injuries, trauma, or surgeries that reduce your balance, mobility or strength? (no)
- Do you use an assistive device such as a cane or walker? (no)

A study team member will measure the subject's height and mass. The subject's clinic number, birth date, gender, and preferred-kicking limb will be recorded.

The protocol is as follows:

Four reflective markers will be placed bilaterally on the subject's heel and toe. Additional markers will be placed on the treadmill belts. The three-dimensional trajectories of each marker will be recorded with a motion capture system (Motion Analysis Corporation, Santa Rosa, CA). Marker trajectories will be used to determine foot placement. While subjects are on the instrumented treadmill, force sensors in the treadmill will record ground reaction forces.

Subjects will walk on a treadmill for a period of up to 15 minutes. The walking speed will not be greater than 3.0 m/s (Diedrich et al., *Journal of Experimental Psychology*, 21:183-202, 1995). The purpose of this walking trial is to provide a period of warming up and familiarization with the treadmill.

The subjects will respond to external disturbances delivered by treadmill which has been programmed to provide the same disturbances as a commercially available, computer-controlled treadmill that is used clinically (CPT Codes: 97750, 97110, 97112, and 97116) for balance assessments and training (ActiveStep, Simbex, Lebanon, NH, <http://activestep.simbex.com/>). Before disturbances are delivered, subjects will be securely harnessed to an overhead rail so that the subject's knees and hands cannot

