touch the treadmill. These methods are similar to other protocols in progress or in completion (IRB 11-006984, IRB 12-002515, IRB 13-000605, IRB 14-000939, IRB 15-004618, IRB 15-005602, IRB 16-000754, IRB 16-002999, IRB 19-007775). A maximum of 50 disturbances will be delivered.

The testing session will be video recorded as a method of study quality control to help study staff determine if a fall occurred during a treadmill disturbance. If a video clip of the testing will be used for presentation purposes, the volunteer's face will be concealed to protect their privacy.

The dependent variables from this assessment are the treadmill belt displacements, belt peak velocities, treadmill force, treadmill moment, center of pressure, and initial belt accelerations.

Subjects will be allowed to rest at their request. The protocol will be video recorded for documentation purposes.

**Resources:** *Describe the available resources to conduct the research (personnel, time, facilities, mentor commitment, etc.):* The Motion Analysis Laboratory contains all equipment listed in the protocol. Three engineers are assigned to the project to run the data collection trials, process data, and disseminate the results through presentations and manuscripts.

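### The ±0.11 SD precision for the limits of agreement counts 20 subjects × 50 repeated trials as 1000 independent differences

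*Protocol*

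**What the plan says.** The Power Statement (Protocol, Data Analysis) reads "20 subjects will each perform 50 trials (1000 data points for each treadmill"). It continues "With 1000 data points, we can accurately estimate the limits of agreement to within" ±0.11 standard deviations, citing the usual large-sample formula for a limit of agreement.

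Three other places describe the design behind that n:

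- Subject Information: "Target accrual: 20 healthy adults".
- Study Design and Methods: "Subjects will participate for a single 2 hour visit", and "A maximum of 50 disturbances will be delivered". The count of 1000 is therefore the most the study can yield.
- Research Question and Aims: accuracy is to be judged "under real world use scenarios (i.e., with a subject on the treadmill belt"), and the hypothesis is that "a Bland-Altman plot 95% confidence interval of differences between input and observed characteristics will contain zero".

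The protocol states no within-subject correlation, no design effect and no assumption that trials are independent.

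**The concern.** The variance 3s²/n for a limit of agreement holds for n independent differences. Here the differences are nested: up to 50 come from the same person on the same belt in the same session. Anything about the person that shifts belt error, such as body mass or the way they step, is shared by all of that person's trials. The aim of testing with a person on the belt makes such an effect a live possibility. The measured variables also include force, moment and center of pressure, and the single n = 1000 figure is applied without distinguishing between them.

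The ±0.11 SD is the protocol's only stated precision and its only quantitative support for the sample size. If it is too optimistic, readers will think the limits are better determined than they are. If the final intervals are also computed on n = 1000, they will be too narrow.

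The effect on the hypothesis depends on how its zero-containing interval is read. If it is a confidence interval for the mean difference computed on n = 1000, an unbiased treadmill would fail more often than 5% of the time. If it is the limits of agreement themselves, clustering has practically no effect on the rule.

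**Working it through.** **Inputs.** k = 20 subjects (Subject Information); m = 50 trials per subject and n = 1000 (Power Statement); m is a maximum (Study Design and Methods). The ICC is not given, so a range is assumed.

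**Reproducing the stated figure.** 1.96 × √(3/1000) = 0.107, which rounds to 0.11. The extracted text shows a 2 beside the root. Read as a multiplier it would give 1.96 × √(6/1000) = 0.152, which does not match. It is taken as the root index and is not counted as an error.

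**Allowing for clustering.** Take a balanced one-way random-effects model with total variance 1, between-subject variance ICC and within-subject variance 1 − ICC.

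- MSB = (1 − ICC) + 50 × ICC, on 19 df; MSW = 1 − ICC, on 980 df
- Var(mean) = MSB/1000
- Var(total variance) = (1/50²) × 2 × MSB²/19 + (49/50)² × 2 × MSW²/980
- Var(SD) = Var(total variance)/4
- Half-width = 1.96 × √[Var(mean) + 1.96² × Var(SD)]

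Example at ICC 0.10: MSB = 0.9 + 5 = 5.9 and Var(mean) = 0.0059. Var(total variance) = 0.00147 + 0.00159 = 0.00305, so Var(SD) = 0.00076. Half-width = 1.96 × √(0.0059 + 3.8416 × 0.00076) = 0.184.

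The equivalent number of independent differences is 3 × 1.96²/half-width².

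| ICC (assumed) | Half-width, SD | Equivalent n |
|---|---|---|
| 0 | 0.106 | about 1000 |
| 0.01 | 0.115 | – |
| 0.02 | 0.123 | – |
| 0.05 | 0.147 | 533 |
| 0.10 | 0.184 | 340 |
| 0.20 | 0.253 | 179 |
| 0.50 | 0.448 | – |

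The theoretical ceiling, when only the 20 subjects carry information, is 0.76. The half-width stops rounding to 0.11 at an ICC of about 0.01. Simulation of the pooled limit agrees: 0.107, 0.145 and 0.186 at ICC 0, 0.05 and 0.10.

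Applying the simple design effect 1 + 49 × ICC to n gives wider values (0.20 at ICC 0.05, 0.26 at 0.10). The table uses the less pessimistic calculation.

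**Coverage if intervals are computed on n = 1000** (20,000 simulated studies per ICC, nominal 95%):

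| ICC | Interval for a limit | Interval for the mean |
|---|---|---|
| 0 | 95% | 95% |
| 0.01 | 93% | 89% |
| 0.02 | 91% | 84% |
| 0.05 | 85% | 71% |
| 0.10 | 75% | 58% |
| 0.20 | 60% | 45% |

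The limits of agreement themselves contained zero in every simulated unbiased study up to ICC 0.50.

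**Fewer trials.** With 40 trials per subject (assumed) the half-width is 0.118 at ICC 0 and 0.258 at ICC 0.20. The ICC matters far more than a shortfall in trials.

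**The case against.** The strongest reply is that the quantity measured is the error of a machine, not a subject's response. A computer-controlled belt may err in much the same way whoever stands on it. The ICC could then be near zero and 0.11 nearly right. This stands as a statement about size: no figure in the protocol supports any particular ICC, and the values at 0.50 and the ceiling are extremes, not expectations. It does not justify stating the precision without condition in a study designed to test the belt under human load.

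A second reply is that the one-way model may not fit. If belt error differs by commanded magnitude and every subject receives the same set, part of the spread is fixed by design and the precision can even be better than stated. With 80% of the variance between levels and 2% between subjects, a simulation gave about 0.08 SD; with 50% and 5% it gave 0.13 SD. The table is indeed model-dependent. But the protocol gives no such schedule, and the stated figure does not rest on that model either.

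Third, the protocol does not say that the final intervals will use n = 1000, and the estimator may be set out in a statistical analysis plan that was not available here. The coverage figures are accordingly conditional. A later choice of analysis would not correct the precision the protocol states now.

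Finally, the protocol sets no target width or agreement margin, so no decision depends on 0.11. That limits the consequence but leaves the figure unsupported.

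**Conclusion.** The concern holds. The ±0.11 SD follows from treating 1000 clustered observations as independent, and the protocol offers no ground for doing so. Strictly it requires ICC 0; to two decimals it survives up to about 0.01. From about 0.05 upward the limits are clearly less precise than stated, and at ICC 0.20 the half-width is more than double (0.253 against 0.107).

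That the stated n ignores clustering does not depend on any assumption; the size of the loss does. It rests on an assumed ICC, a one-way model with subject as the only source of clustering, and the full 50 trials per subject. The coverage losses apply only if intervals are computed on n = 1000. This should be fixed, but it does not threaten the feasibility of the study.

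**What to change.** In the Power Statement, describe the design as 20 subjects with up to 50 repeated trials each, and replace the single figure by a range over the ICC, for example ±0.11 SD at ICC 0 to about ±0.25 SD at ICC 0.20. If independence is to be assumed for some variables, say so and give the reason.

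Estimate the bias, the limits of agreement and their confidence intervals with a repeated-measures Bland-Altman method: a random effect for subject, limits built from between- plus within-subject variance, and intervals with the subject as the sampling unit.

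The cost is a change of wording, slightly more analysis work and a less favourable stated precision. Since the protocol sets no target width, the restatement calls for no extra subjects.

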#### Endpoints

Primary: Complete data collection of all subjects and complete statistical analyses

Secondary: Manuscript publication
